#### **4. Objectives**

1a: To identify the demographic and behavioural risk factors associated with incident HIV infection (based on “NAT yield” or LAg Avidity testing) among blood donors in South Africa.

Hypotheses: 1) The risk factors for incident HIV in blood donors in South Africa will include a recent change in sexual partner, older male/younger female sexual partnership, a greater number of recent sexual partners, unprotected receptive anal intercourse, and lower socioeconomic status.

1b: To identify the demographic and behavioural risk factors associated with incident HBV infection among blood donors in South Africa identified as “NAT-yields” or concordant serology and NAT positive and anti-HBc negative.

Hypotheses: 1) The risk factors for incident HBV in blood donors in South Africa will include greater number of recent sexual partners, recent scarification/tattoo/body markings, and history of personal contact with an HBV-infected person.

2a: To determine HIV subtype and drug resistance profiles among HIV positive donors with recently acquired infection based on year of donation and site of collection, and examine findings with donor demographics and risk behaviors derived in Objective 1.

Hypotheses: 1) The proportion of donors identified with incident HIV infection containing drug resistance mutations will be positively related to the proportion of HIV-positive individuals receiving anti-retroviral therapy at a population-level in South Africa

2b: To determine HBV genotype profiles among HBV positive donors with recently acquired infection based on year of donation and site of collection, and correlate findings with donor demographics and risk behaviors derived in Objective 1

Hypotheses: 1) Incident HBV infections will show differences in genotypes with genotype E increasing when compared to public health data on prevalent infections.

3: To prospectively characterize the virology, immunology and natural history of incident HIV infection among a cohort of recently infected blood donors and a small group of elite controllers in South Africa.

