The purpose of objective 1a is to identify the demographic and behavioural risk factors associated with incident HIV infection among blood donors in South Africa previously identified as “NAT-yield” and other recently acquired infection based on LAg Avidity testing as compared to controls. The outcome variable is whether or not a blood donor has HIV infection. That is, a binomial variable. The predictor variables believed to be associated with HIV in blood donors will include recent change in sexual partner, older male/younger female sexual partnership, a greater number of recent sexual partners, unprotected receptive anal intercourse, and lower socioeconomic status. Other possible predictor variables, e.g., behavioural variables, will be examined to understand their relationship to whether or not the blood donor has HIV infection. The association between the outcome variable and a predictor variable will be examined using categorical data analysis techniques. Bivariate analysis will be conducted using Chi-square tests. Analyses that include more than one predictor variable will be conducted using multiple logistic regression, which may include interaction terms. In addition, nonparametric modeling will be used when there are multiple predictor variables.

The purpose of objective 1b is to identify the demographic and behavioural risk factors associated with incident HBV infection among blood donors in South Africa previously identified as “NAT-yields” and which are anti-HBc negative. The outcome variable is whether or not blood donor has HBV infection. That is, a binomial variable. The predictor variables believed to be associated with HIV in blood donors will include greater number of recent sexual partners, recent scarification/tattoo/body markings, and history of personal contact with an HBV-infected

person. Other possible predictor variables, e.g., demographic variables, will be examined to understand their relationship to whether or not the blood donor has HBV infection. The association between the outcome variable and predictor variable will be examined using categorical data analysis techniques. Bivariate analysis will be conducted using Chi-square tests. Analyses that include more than one predictor variable will be conducted using multiple logistic regression, which may include interaction terms. In addition, nonparametric modeling will be used when there are multiple predictor variables.

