***If F12 is not equal to 1, skip to F14***

F13a. Does partner 1 take HIV medications? (Choose one)

- 0 No
- 1 Yes
- 97 Don't Know
- 98 Refuse to Answer

F14. Does partner 1 have hepatitis?

- 1 Yes
- 2 No
- 97 Don't Know
- 98 Refused to answer

F15. Did you become sexually involved with partner 1 because you thought that he/she would provide you with some material benefit that you wanted or needed, such as food, shelter, transport, school fees, or other goods?

- 0 No
- 1 Yes
- 97 Don't Know
- 98 Refuse to Answer
- 99 Not Applicable

F15a. If yes, can you tell us what you wanted or needed? It could be food, clothes, transport, school fees, residence, fees, somewhere to stay or sleep, alcohol, drugs, cash or something else.

---

F16. Where did you first meet partner 1? (Choose one)

- 1 Bar, nightclub, restaurant, tavern, shebeen, coffee shop
- 2 Strip club, "Adults Only" club, sex club
- 3 Street, park, library, public transportation, minibus taxi, train
- 4 Party, braai, political function, stokvel or church
- 5 Internet
- 6 Dating service, newspaper ads
- 7 Gym, sports event
- 8 School, technicon, university, college
- 9 Work
- 10 Met some other way
- 97 Don't Know
- 98 Refuse to Answer

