**SECTION I - MEDICAL HISTORY**

**READ and HEARD:** *In the next set of questions we will ask about some medical treatments you may have had.*

I1. Have you ever had a blood transfusion? (Choose one)

- 0 No **Skip to I5**
- 1 Yes
- 97 Don't Know
- 98 Refuse to Answer

I2. How many transfusion episodes have you had?

— —

- 97 Don't Know
- 98 Refuse to Answer

I3. When was the first year you received a transfusion?

— — — —

- 9997 Don't Know
- 9998 Refuse to Answer

**If I3 is less than B2 then READ and HEARD:** *"The year that you entered for first year transfusion is smaller than the year you were born. Please correct the year of your first transfusion." (Returns to I3)*

14. When was the last year you received a transfusion?

— — — —

9997 Don't Know

9998 Refuse to Answer

***If 14 is less than 13 then READ and HEARD: "The year that you entered for last year of transfusion is smaller than the year of your first reported transfusion. Please correct the last year of your transfusion." (Returns to 14)***

15. Have you ever had minor or major surgery in a hospital, doctor's room, or dentist's office? (Choose one)

0 No ***Skip to 19***

1 Yes

97 Don't Know

98 Refuse to Answer

16. In the 6 months before your donation, have you had minor or major medical surgery in hospital? (Choose one)

0 No

1 Yes

97 Don't Know

98 Refuse to Answer

17. In the 6 months before your donation, have you had any surgical procedures in your doctor's room or office? (Choose one)

- 0 No
- 1 Yes
- 97 Don't Know
- 98 Refuse to Answer

18. In the 6 months before your donation, have you had any tooth extractions or another dental procedure at a dentist's office? (Choose one)

- 0 No
- 1 Yes
- 97 Don't Know
- 98 Refuse to Answer

19. Have you ever had an endoscopy (a medical test where a flexible tube is used to look inside of your throat and digestive system) or colonoscopy (a medical test where tube is used to look inside your colon/large intestine)? (Choose one)

- 0 No **Skip to I11**
- 1 Yes
- 97 Don't Know
- 98 Refuse to Answer

I10. In the 6 months before your donation, have you had an endoscopy or colonoscopy? (Choose one)

- 0 No
- 1 Yes
- 7 Don't Know
- 8 Refuse to Answer

I11. Have you ever been immunized / vaccinated against Hepatitis B?

- 0 No
- 1 Yes
- 97 Don't Know
- 98 Refuse to Answer

I11b. If yes, can you tell us your age when you were immunized/vaccinated against Hepatitis B?

\_\_\_\_\_ years old

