- 6 A gel used as part of a research study
- 7 Other (please specify); \_\_\_\_\_

J18a. In the 6 months before your donation, have you had Raatib, ritual scarring, ritual piercing, ritual circumcision, blood sharing or been stabbed?

- |    |                  |                    |
|----|------------------|--------------------|
| 0  | No               | Skip to J20 |
| 1  | Yes              |                    |
| 97 | Don't Know       |                    |
| 98 | Refuse to Answer |                    |

J18b. Can you please tell us which activity? (Check all that apply)

- 1 Raatib
- 2 Ritual scarring
- 3 Ritual piercing
- 4 Ritual circumcision
- 5 Blood sharing
- 6 Been stabbed
- 7 Other (please specify); \_\_\_\_\_

J19. What was the reason for the activity?

- 1 Cultural, ritual, religious
- 2 Administering a substance in my skin for treatment or prevention
- 3 Letting out blood
- 4 Sealing a "blood pact"
- 5 Other

97 Don't Know

98 Refuse to Answer

J20. In the 6 months before your donation, did you visit a traditional healer and receive traditional medicine other than cuts and/or scarification?

0 No

1 Yes

97 Don't Know

98 Refuse to Answer

J21. In the 6 months before your donation, did you live in an environment where you were frequently bitten by mosquitos?

0 No

1 Yes

97 Don't Know

98 Refuse to Answer

J22. In the 6 months prior to your last donation, did you live in an environment where you were frequently bitten by bed bugs or lice?

- 0 No
- 1 Yes
- 97 Don't Know
- 98 Refuse to Answer

J23. In the 6 months prior to your last donation, did you have an injury such as a knife or stab wound or were you in an accident where you lost blood from a cut or injury?

- 0 No
- 1 Yes
- 97 Don't Know
- 98 Refuse to Answer

**READ and HEARD:** Now, we would like to know about any personal contact you have had with persons who have HIV or hepatitis. In each question, please include only family members, personal friends or acquaintances. (If you are a health care worker, please do NOT include any individuals you have given professional care to, we will ask about those contacts in a minute).

J31. How many people do you personally know who do NOT have AIDS, but have tested positive for HIV, the virus that causes AIDS? (Choose one)

- 0      0 (none)
- 1      1
- 2      2 to 4
- 3      5 or more
- 97     Don't Know
- 98     Refuse to Answer

J32. How many people do you personally know who currently have AIDS or have died of AIDS? (Choose one)

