- 0      0 (none)
- 1      1
- 2      2 to 4
- 3      5 or more
- 97     Don't Know
- 98     Refuse to Answer

J33. How many people do you personally know who have hepatitis? (Choose one)

- 0 0 (none)
- 1 1
- 2 2 to 4
- 3 5 or more
- 97 Don't Know
- 98 Refuse to Answer

J34. How many people do you personally know who have died of hepatitis? (Choose one)

- 0 0 (none)
- 1 1
- 2 2 to 4
- 3 5 or more
- 97 Don't Know
- 98 Refuse to Answer

J35. In the 6 months have you been in close contact with anybody who had Hepatitis (yellow jaundice), e.g. people you live or work with?

- 0 No
- 1 Yes
- 97 Don't Know
- 98 Refuse to Answer

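### Hypothesis 1b is about contact with an HBV-infected person, but the contact items record hepatitis of any type, so a result cannot be attributed to HBV contact

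*Protocol*

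**What the plan says.** Section 4 (Objectives), hypothesis 1b, names "history of personal contact with an HBV-infected person" beside number of recent sexual partners and recent body marking. Section 4.9 (Analytic Approach) carries the same list into the Objective 1b analysis, "recent scarification/tattoo/body markings, and history of personal contact with an HBV-infected" person, to be tested by chi-square and multiple logistic regression.

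Appendix 7 has four items on contact with hepatitis that cases and controls both answer:

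- F14, repeated for up to five partners: "Does partner 1 have hepatitis"
- J33: "How many people do you personally know who have hepatitis"
- J34: "How many people do you personally know who have died of hepatitis"
- J35, the only close-contact item: "have you been in close contact with anybody who had Hepatitis (yellow jaundice), e.g. people you live or work with"

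The lead-in to the Section J block is equally general: "any personal contact you have had with persons who have HIV or hepatitis". The same questionnaire does name the virus elsewhere. I11 asks "Have you ever been immunized / vaccinated against Hepatitis B", and L9 asks HBV cases, in free text, how they think they were infected with HBV.

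**The concern.** The hypothesis and the planned predictor concern one virus. The items record a broader category, in which a contact with hepatitis A, hepatitis C or jaundice from a non-viral cause is coded exactly like a contact with hepatitis B. A positive finding could not be read as evidence about HBV contact, and a null finding could reflect either no effect or an HBV effect masked by irrelevant contacts.

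This cannot be left to an analysis plan, because no analysis can recover a type that was never asked. At stake is one of the three named 1b hypotheses. The other two, and Objective 1a, are unaffected.

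**Working it through.** **1. Is there an HBV-specific contact item anywhere in Appendix 7?**

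| Item | Asks about | Usable as HBV contact, cases against controls? |
|---|---|---|
| F14 | Partner's hepatitis, no type | Not type-specific |
| J33, J34 | People known who have, or died of, hepatitis | Not type-specific; acquaintance, no time window |
| J35 | Close contact, hepatitis or yellow jaundice | Not type-specific |
| F12, G2a, G2b | Partner's HIV status | HIV only; Section G has no HBV item |
| I11 | Respondent's own hepatitis B vaccination | Not a contact item |
| L9 | Believed source of own HBV infection | HBV cases only, free text |
| K1 to K3 | Body fluids, needlesticks, splashes at work | Does not ask the contact's HBV status |

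There is none. Item numbers jump from J23 to J31, but the lead-in to the contact block comes after that gap, so the gap does not suggest a lost HBV contact item.

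**2. The plan's own figures.** The protocol states no detectable odds ratio for HBV contact. Table 9 (1.87, 1.90, 1.96 at 150 cases and 450 controls) is for scarification and similar body modification at 45 to 55% control exposure. Its tabulated proportions give 1.83, 1.86 and 1.91 directly. The stated values come from a clustered simulation whose correlation inputs are not given, so they can be neither reproduced nor called wrong. Nothing below depends on them.

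**3. Effect under equal misclassification.** Assumptions, none from the protocol: p = HBV contact in controls; true odds ratio 2.0; q = unrelated hepatitis or jaundice contact, the same in both groups and independent of HBV contact.

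- HBV contact in cases: p1 = 2p / (1 − p + 2p)
- Any-hepatitis contact in each group: 1 − (1 − HBV contact)(1 − q)

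For p = 5% and q = 5%:

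- p1 = 0.10 / 1.05 = 0.0952
- controls: 1 − 0.95 × 0.95 = 0.0975
- cases: 1 − 0.9048 × 0.95 = 0.1405
- observed odds ratio: (0.1405 / 0.8595) / (0.0975 / 0.9025) = 1.51

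| p | q = 2.5% | q = 5% | q = 10% |
|---|---|---|---|
| 3% | 1.55 | 1.38 | 1.24 |
| 5% | 1.68 | 1.51 | 1.34 |
| 10% | 1.82 | 1.69 | 1.53 |

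A second calculation, with a true odds ratio of 1.90 and reporting sensitivity of 0.8 to 1.0, also moved towards 1 in every scenario with false positives (1.12 to 1.76 over p of 2 to 10% and false positives of 2 to 10%).

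**4. Effect if cases over-report.** Section 4.2.2 (Participant Enrollment) has cases told of likely HIV or HBV infection at the visit where the interview is planned. Assume p = 5%, and false-positive contact in 5% of unexposed controls but 10% of unexposed cases.

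- True odds ratio 1.0: controls 0.05 + 0.05 × 0.95 = 0.0975; cases 0.05 + 0.10 × 0.95 = 0.145; observed (0.145 / 0.855) / (0.0975 / 0.9025) = 1.57
- True odds ratio 2.0: cases 0.0952 + 0.10 × 0.9048 = 0.1857; observed (0.1857 / 0.8143) / (0.0975 / 0.9025) = 2.11

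The direction of the error is therefore not fixed by the wording alone.

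**5. Power.** Simple two-proportion test, two-sided alpha 0.05, 150 to 450, no clustering: power = Φ[(d − 1.96·se0) / se1], with d the difference in proportions, se0 the pooled and se1 the unpooled standard error. For p = 5% and no misclassification, d = 0.0452, se0 = 0.0226 and se1 = 0.0261, which gives 51%. The same formula gives 37% at p = 3% and 74% at p = 10%. With the present wording and q = 5%, the 51% becomes 32%.

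**The case against.** Four points deserve weight.

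- **HBV contacts are captured.** A reader might infer that the exposure is not measured at all. The items do not support that: a donor with an HBV-infected partner or household member can say so in F14 or J35. What is missing is the type. This stands and limits the claim.
- **Dilution is conditional.** A reader might take it as certain that the odds ratio is pulled towards 1. That needs equal misclassification in cases and controls, and the protocol's order of disclosure and interview makes unequal reporting plausible. This stands. Over-reporting is a separate problem, however, and would not make the result attributable to HBV contact.
- **Power is limited anyway.** It is tempting to set the diluted odds ratios against the 1.6 to 2.0 range in Section 4.8 and conclude that the wording makes the effect undetectable. That range pools HIV and HBV. Its lower end comes from 300 HIV cases at 25% control exposure. At 3 to 10% exposure, 150 HBV cases fall short of 80% power for an odds ratio of 2.0 even with perfect wording. The comparison does not isolate harm from the wording.
- **Lay respondents may not know the type.** In the 5% and 5% scenario, if only half of true HBV contacts are reported as type B (an assumption), an HBV-specific item has 31% power against 32% for the present item. At 10% HBV contact it is 45% against 60%. A specific item thus buys interpretability (odds ratio about 1.9 to 1.95 for a true 2.0), not clearly power. Broad wording could be a defensible choice, although the protocol does not give that reason. A follow-up that leaves the broad stem in place avoids the trade-off.

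**Conclusion.** The mismatch is real and rests on the text alone: hypothesis 1b and its analysis name HBV, while no contact item asked of both cases and controls identifies it. The stated predictor cannot be built from these data. Only contact with any hepatitis or jaundice can.

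The numerical size is illustrative, because the protocol gives no prevalence of HBV contact or of other hepatitis contact. Under equal misclassification and the assumptions above, a true odds ratio of 2.0 appears as 1.24 to 1.82, about 1.5 in the central case. Over-reporting by cases could move it the other way. The point is worth correcting because the correction is cheap and restores one of three named hypotheses. It does not call the rest of Objective 1b into question.

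**What to change.** Keep the present stems of F14 and J33 to J35 and add one follow-up on each: which type, with answers A, B, C, other, and type not known. Remove the yellow-jaundice gloss from J35. Test hypothesis 1b on the hepatitis B answers, with type not known as a separate level, and keep any-hepatitis contact as a secondary variable.

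If the items are not changed, restate the 1b predictor in Sections 4 and 4.9 as contact with a person with hepatitis of any type, and interpret it as such.

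The cost is one extra response field on each of these items in the computer-assisted interview. Some respondents will not know the type, which thins the hepatitis B category, but the broad variable remains available for them. The follow-up does not address differential recall.

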#### **4.2.2. Control Recruitment and Enrollment**

SANBS collection sites are administratively organized into zones, branches, and clinic sites. Clinics can be fixed or mobile collection sites. To meet the study criterion of matching by geographic area, controls will be selected from clinics within the branches from where persons with recently acquired HIV infection have been identified. To minimize selection bias, clinics within each branch will be randomly selected by the study statisticians. On recruitment days at the randomly selected clinics, individuals that are demographically matched potential controls (age within 5 years, and by population group) will be randomly selected using systematic sampling and approached for enrollment into the study as a “potential control”. Our study documents and consents indicate the “potential control” designation, and explain the meaning of this term. Following successful donation the potential controls will be invited to complete the ACASI study questionnaire. After each donation has been tested and if the donor tests negative for all infections, the person will be reclassified in the database as a control.

The characteristics of individuals with recent HIV and HBV infection (per NAT-only over a 5 year period) are substantially similar for the three matching variables for the study cases and controls (see Table 3). As such, we intend to use a subset of the controls matched for the HIV portion of the study to serve as controls for the HBV objective.

Table 3. Demographic characteristics of HIV NAT only and HBV NAT only positive donors at SANBS for the years 2006 – 2010.

Demographic Characteristic		HIV (n=300)		HBV (n=248)	
		Number	Percent	Number	Percent
Gender	Female	174	58.0	108	43.5
	Male	126	42.0	139	56.0
	Missing	0	0.0	1	0.4
Population Group	Asian	6	2.0	12	4.8
	Black	251	83.7	161	64.9
	Coloured	12	4.0	10	4.0
	White	29	9.7	63	25.4
	Missing	2	0.7	0	0.0
Age Group	16-19 years	49	16.3	43	17.3
	20-25	90	30.0	69	27.8
	26-30	59	19.7	43	17.3
	31-40	60	20.0	52	21.0
	41-50	32	10.7	24	9.7
	51-60	10	3.3	10	4.0
	61-70	0	0.0	7	2.8
SANBS Region	Eastern Cape	24	8.0	18	7.3
	Egoli (Johannesburg)	43	14.3	34	13.7
	Free State/Northern Cape	29	9.7	28	11.3
	KwaZulu Natal (Durban)	83	27.7	60	24.2
	Mpumalanga	35	11.7	30	12.1
	Northern (Pretoria)	52	17.3	31	12.5
	Vaal	34	11.3	47	19.0

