Clear information will be provided to participants on the visit schedule, including the enrollment visit expected to occur approximately 1 month after the index donation visit and repeat sampling at 3 follow-up visits at 2, 3, and 6 months following the index blood donation. The importance of adherence to the visit schedule will be emphasized, and full contact details recorded for each participant. Follow-up contact of these donors will be centrally coordinated and each MLO notified when a donor in the prospective cohort must be contacted to return for follow-up samples. Donors will be contacted via telephone. During this telephone call, an appointment will be made for the donor to return for follow-up testing at a specific date, time and venue. If the donor cannot, after repeated attempts, be contacted via telephone, a letter and text message will be sent to the donor. If the donor were to respond to the letter or text message, an appointment will be confirmed for that donor. Letters confirming the date, time and venue of the appointment will be sent to each donor and will be followed by a text message the day before the appointment. All successful and unsuccessful contact attempts with the participant will be documented in a Contact Log, as described above. At scheduled follow-up visits, participant samples will be collected, labeled and sent to the Donation Testing Laboratory in Constantia Kloof as detailed above.

Every year SANBS identifies approximately 50 NAT-only HIV infections. With a planned enrollment period of 3 years and an enrollment target of 50 HIV NAT-only infections for

Objective 3, and assuming 50% enrollment, we anticipate two years of accrual to meet the enrollment goal, and allow 6 months of prospective follow up.

[figure not shown]
The number of elite controllers identified each year has been increasing (Table 4). Projecting that the proportion of donors who are elite controllers in 2014 -2017 will be similar to those observed in recent years and assuming a 50% enrollment rate it will be feasible to enroll 20 elite controllers during the first 2.5 years of the study, allowing for a tail-end follow-up of 6 additional months of return follow-up visits during the same time as the Objective 1 and 2 enrollment takes place.

Table 4. Number of elite controller HIV infections identified each year by SANBS while ID-NAT for HIV has been in use.

Year	Elite Controllers
2007	2
2008	11
2009	8
2010	9
2011	13
2012	21

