### **4.4 Measurement**

#### **4.4.1 Schedule of Measurement**

**Risk Factor Questionnaire:** A new questionnaire for the South Africa setting has been developed in English from a template previously used in Brazil for the REDS-II study. It assesses risk exposure over two intervals; ever and within the 6 months preceding the index donation. **Appendix 7** provides content for the risk factor questionnaire. The interview will be an audio computer-assisted structured interview (ACASI) as done successfully in a previous REDS-II and current REDS-III study in Brazil. Participants will be able to read and hear the questions using

ear phones for privacy. Interviews will be conducted using portable laptops so as to provide ease of access to the study participants. The ACASI interview will be conducted in a private location, ideally at a SANBS blood centre, but we will allow the interview to be conducted at the study participants' location of preference, such as at home. We propose to use 10 laptop computers (2 per zone) which will permit simultaneous interviews at different locations throughout SANBS. It will take approximately 30-45 minutes to complete the questionnaire. Interview data will be backed-up from the laptops onto a server or dedicated desktop computer at SANBS central offices on a daily basis, and uploaded weekly via a secure FTP site to the Data Coordinating Centre.

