- 5 Business/sales/retail
- 6 Farming
- 7 Teacher/ education/ student
- 8 General labour (domestic worker, gardener, janitorial)
- 9 Civil service (examples including working in government office, post office)
- 10 Other
- 97 Don't Know
- 98 Refuse to Answer

B13c. *If B13b=10 Else SKIP* What is your occupation?

-----

B14a. In the last 6 months have you spent a total of four weeks or more away from your primary residence (home)?

- 0 No
- 1 Yes
- 97 Don't Know
- 98 Refuse to Answer

*If B14a equals 0, then skip to B15a.*

B14b. What was the primary purpose for being away during this period?

- 1 Work

- 2 Looking for work
- 3 Holiday
- 4 Other, specify: \_\_\_\_\_

B15a. How many nights did you sleep at your primary residence (home) in the past six months?

- 1 Every night
- 2 Most nights
- 3 About half of the nights
- 4 Fewer than half of the nights

B15b. How long has your pattern of sleeping at your primary residence (home) been the same as it has been in the past six months?

- 1 It has been like this only in the past 6 months
- 2 It has been like this for only the past year
- 3 For one to five years
- 4 For five years or more

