***If F1a is equal to 1 and F1b is equal to 0, then skip to Section G.***

F12. What is partner 1's HIV status? (Choose one)

- 1 Positive
- 2 Negative
- 3 Unknown
- 98 Refuse to Answer

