***If F21 is equal to none, then skip to F24.***

F22. When you had insertive anal sex, how frequently did you use condoms? (Choose one)

- never
- some times
- every time
- Don't Know
- Refuse to Answer

F23. Number of times you had receptive anal sex (partner 1 inserted his penis into your anus) in the past 6 months. (Choose one)

- none
- 1 to 3 times
- 4 to 10 times
- more than 10 times
- Don't Know
- Refuse to Answer

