***If F23 is equal to 0, then skip to F25.***

F24. When you had receptive anal sex, how frequently did you use condoms? (Choose one)

- never
- some times
- every time
- Don't Know
- Refuse to Answer

F25. Number of times you had oral sex with partner 1 in past 6 months

- none
- 1 to 3 times
- 4 to 10 times
- more than 10 times
- Don't Know
- Refuse to Answer

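### Five questionnaire items, including those on receptive anal sex and close hepatitis contact, are not tied to the index donation as section 4.4.1 requires, so the exposure window can differ between cases and controls

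*Protocol*

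**What the plan says.** Protocol section 4.4.1, on the risk factor questionnaire, fixes the reference periods: "It assesses risk exposure over two intervals; ever and within the 6 months preceding the index donation".

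Five items in Appendix 7 do not follow this:

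- F23, receptive anal sex: "F23. Number of times you had receptive anal sex (partner 1 inserted his penis into your anus) in the past 6 months". F24, on condom use during receptive anal sex, has no window of its own and takes F23's.
- F25, oral sex: "F25. Number of times you had oral sex with partner 1 in past 6 months".
- B14a, time away from home: "B14a. In the last 6 months have you spent a total of four weeks or more away from your primary residence (home". B15a, nights slept at home, also uses the past six months.
- J35, hepatitis contact: "J35. In the 6 months have you been in close contact with anybody who had Hepatitis (yellow jaundice". Neither the donation nor the interview is named.

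On timing, the section on control recruitment and enrolment says: "Following successful donation the potential controls will be invited to complete the ACASI study questionnaire". Section 4.2.2 (Participant Enrollment) has cases consent at the retest visit after recall and then complete the interview, with the option of coming back later. The only figure for the delay is in the Objective 3 text: "enrollment visit expected to occur approximately 1 month after the index donation visit".

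**The concern.** Objective 1 compares exposure in incident cases with exposure in marker-negative controls. The comparison needs the same window, relative to the donation, in both groups. If an item looks back from the interview, a control interviewed on the donation day reports the 6 months before donation. A case interviewed a month later reports about 5 months before and 1 month after. The earliest month drops out and a month that cannot have contributed to the detected infection enters, in cases only.

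Two of the affected items matter for section 4. Unprotected receptive anal intercourse is a hypothesised HIV risk factor, measured by F23 and F24. Personal contact with an HBV-infected person is a hypothesised HBV risk factor, and J35 bears on it. These items record no dates of the acts or contacts, so the analysis could not move the answers back to the intended window.

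**Working it through.** There is no stated figure to reproduce. The check compares item wording with section 4.4.1 and then sizes the shift.

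**Anchoring of items that serve a section 4 hypothesis**

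| Exposure | Item | Reference period as worded |
|---|---|---|
| Number of recent partners | F2 | before donation |
| Tattoo, piercing | J6, J9 | before donation |
| Ritual scarring | J18a | before donation |
| Receptive anal sex, condom use | F23, F24 | past 6 months |
| Close hepatitis contact | J35 | 6 months, no anchor |

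F17, F19 and F21, in the same block as F23, all refer to the period before donation.

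**Share of the window displaced**

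Share = lag / 6 months, taking 6 months as 182.6 days. The lags are assumptions except for the 1 month stated for Objective 3.

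- 2 weeks: 14 / 182.6 = 8%
- 1 month: 1 / 6 = 17%
- 2 months: 2 / 6 = 33%

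**Effect on the F23 odds ratio**

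F19 asks about anal sex before the donation, and an answer of none skips past F23. To be recorded as exposed on F23, a case must therefore have had anal sex in the 6 months before donation and receptive anal sex in the 6 months before interview.

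Assumptions: true odds ratio 1; sporadic, independent acts; all anal sex receptive; behaviour unchanged after donation; 6-month prevalence p. Write λ = −ln(1 − p)/6 per month and s for the lag in months. Then

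P(recorded in a case) = 1 − 2(1 − p) + exp(−λ(6 + s)).

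For p = 0.20 and s = 1:

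- λ = 0.0372 and exp(−7λ) = 0.7708
- P = 1 − 1.6 + 0.7708 = 0.1708
- odds = 0.206, against control odds of 0.25, so the odds ratio is 0.82

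For p = 0.02 and s = 1 the odds ratio is 0.83. At s = 2 it is 0.67 for both prevalences. If cases stopped entirely on the donation day, the 1-month values would be 0.82 to 0.83, almost the same, because the gate already blocks post-donation-only exposure.

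At the other extreme, someone regularly exposed before donation answers yes under either window, and the odds ratio stays at 1.00. The 1-month range for F23 is therefore roughly 0.8 to 1.0.

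**Effect on an ungated item read as looking back from the interview**

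J35 would be one, if read that way. With k the post-donation exposure rate relative to the pre-donation rate,

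P(case) = 1 − exp(−λ(6 − s + s·k)).

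For s = 1 and p from 0.02 to 0.20:

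| k | Odds ratio at true value 1 |
|---|---|
| 0 (stops at donation) | 0.83 to 0.82 |
| 0.5 | 0.92 to 0.91 |
| 1 (unchanged) | 1.00 |
| 2 | 1.17 to 1.19 |

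Here bias arises only if exposure, or its reporting, changes after the donation. With every item anchored to the donation, the displaced share is 0% and the artefact is 1.00.

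**The case against.** The strongest reply is that this is a lapse in a few items of an evidently unfinished instrument, and that most of the questionnaire is right. Much of that stands.

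- A reader might infer that the hypothesised exposures in general look back from the interview. They do not: partner number, tattoo, piercing and scarring are anchored to the donation, and these include the exposures behind the sample size.
- J35 does not say that it looks back from the interview. Its neighbours J20 to J23 name the donation, so words have probably been dropped. The HBV hypothesis concerns any history of contact, and J33 and F14 bear on it too.
- The 1-month delay is stated only for Objective 3. For other Objective 1 cases the delay is not fixed. Nor is it strictly zero for controls, since sections 4.4.1 and 4.10 allow interviews elsewhere or at another time.
- F19 limits what can enter F23. For women with male partners, F19 and F20 already give a donation-anchored measure. As printed, the skip before F23 also sends anyone answering none to F21 on to F24, so fewer respondents meet F23's window than the model supposes.
- Odds ratios computed with exposure ceasing after recall would need the recall date. The k = 0 case means stopping on the donation day, before any contact.

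A further tempting reading is that partner-status items such as "F12. What is partner 1's HIV status? (Choose one" inflate case exposure because partners are tested after notification. The documents do not establish this. Cases are told of likely infection at the retest visit, and the interview is planned straight after enrolment. That usually leaves little time for partner testing, although the revised notification letter and the option to return later leave some room. No size can be given.

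None of this removes the conflict between the five items and section 4.4.1, or the later interview of cases.

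**Conclusion.** The point holds for five items. F23 (with F24), F25, B14a and B15a contradict the window in section 4.4.1, and J35 fails to state one. Because cases must be tested, contacted and recalled before they are interviewed, the misalignment can differ by case status.

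For F23 the expected direction is downward, with an artefact of roughly 0.8 to 1.0 at a 1-month lag. That rests on assumed prevalence and exposure pattern and on a lag stated only for Objective 3. For J35 the direction is unknown, and the effect depends on how respondents read the item. F25, B14a and B15a carry no stated hypothesis and matter less. Section 4.8 claims power for odds ratios of 1.6 to 2.0, so a distortion towards the upper end of this size would matter for receptive anal intercourse. The multiple-partner and scarification comparisons used for sample size are unaffected.

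**What to change.** Reword F23, F25, B14a, B15a and J35 to ask about *the 6 months before your donation*, as F17, F19 and F21 already do. F24 then takes the right window through F23. This restores the protocol's own definition and needs no design change. The cost is a few words in five items, with F23 and F25 repeated for each partner in the matrix, made before the interview is programmed and cleared.

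Rewording F12 and F14 to refer to the time of donation is optional and not part of this error. Asking what the donor knew or believed then would replace partner status with donor awareness, which is a different construct.
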